5.4 Secondary outcomes measure(s)

- QoL – measured using EORTC QLQ C30, skin-specific Skin Cancer Index (SCI), and Picker Patient Experience 15 questionnaire (PPE-15) (4, 5).
- Distant metastasis-free survival, defined as days from randomisation to the date of distant metastasis or death from any cause.
- OS, defined as days from randomisation to death for any reason.
- Safety /toxicity as measured by common terminology criteria for adverse events (CTCAE) V5.0 scoring system and serious adverse events, including patient-reported outcomes version of the CTCAE.
- Cost-effectiveness determined by health utility using EQ-5D-5L and recording health resource use. Primary economic outcome, cost per quality-adjusted life year (QALY). Secondary economic outcome, resource use and costs (6).

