4. Worried about the cause of skin cancer?	1	2	3	4	5
5. Felt frustrated about your skin cancer?	1	2	3	4	5
6. Worried that your tumour may become a more serious type of skin cancer?	1	2	3	4	5
7. Worried about new skin cancers occurring in the future?	1	2	3	4	5
8. Felt uncomfortable when meeting new people?	1	2	3	4	5
9. Felt concerned that your skin cancer may worry friends or family?	1	2	3	4	5
10. Worried about the length of time before you can go out in the public?	1	2	3	4	5
11. Felt bothered by people's questions related to your skin cancer?	1	2	3	4	5
12. Felt embarrassed by your skin cancer?	1	2	3	4	5
13. Worried about how large the scar will be?	1	2	3	4	5
14. Thought about how skin cancer affects your attractiveness?	1	2	3	4	5
15. Thought about how noticeable the scar will be to others?	1	2	3	4	5

PPE-15

Date Completed:

D	D	M	M	Y	Y	Y	Y
---	---	---	---	---	---	---	---

When completing this questionnaire please answer about any instances occurring since the surgery for your skin cancer.

1. When you had important questions to ask a doctor, did you get answers that you could understand?

- 1 Yes, always
- 2 Yes, sometimes
- 3 No

2. When you had important questions to ask a doctor, did you get answers that you could understand?

- 1. Yes, always
- 2. Yes, sometimes
- 3. No
- 4. I had no need to ask

3. When you had important questions to ask a nurse, did you get answers that you could understand?

- 1 Yes, always
- 2 Yes, sometimes
- 3 No
- 4 I had no need to ask

4. Sometimes in a hospital, one doctor or nurse will say one thing and another will say something quite different. Did this happen to you?

- 1 Yes, often
-

2 Yes, sometimes

3 No

5. If you had any anxieties or fears about your condition or treatment, did a doctor discuss them with you?

1 Yes, completely

2 Yes, to some extent

3 No

4 I didn't have any anxieties or fears

6. Did doctors talk in front of you as if you weren't there?

1 Yes, completely

2 Yes, sometimes

3 No

7. Did you want to be more involved in decisions made about your care and treatment?

1 Yes, definitely

2 Yes, to some extent

3 No

8. Overall, did you feel you were treated with respect and dignity while you were in hospital?

1 Yes, always

2 Yes, sometimes

3 No

9. If you had any anxieties or fears about your condition or treatment, did a nurse discuss them with you?

1 Yes, completely

2 Yes, to some extent

3 No

4 I didn't have any anxieties or fears

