10. Did you find someone on the hospital staff to talk to about your concerns?

1 Yes, definitely

2 Yes, to some extent

3 No

4 I had no concerns

11. Were you ever in pain?

1 Yes

2 No

If Yes... Do you think the hospital staff did everything they could to help control your pain?

1 Yes, definitely

2 Yes, to some extent

3 No

12. If your family or someone else close to you wanted to talk to a doctor, did they have enough opportunity to do so?

- | | | |
|---|--|--------------------------|
| 1 | Yes, definitely |  |
| 2 | Yes, to some extent |  |
| 3 | No |  |
| 4 | No family or friends were involved |  |
| 5 | My family didn't want or need information |  |
| 6 | I didn't want my family or friends to talk to a doctor |  |

13. Did the doctors or nurses give your family or someone close to you all the information they needed to help you recover?

- | | | |
|---|--|--------------------------|
| 1 | Yes, definitely |  |
| 2 | Yes, to some extent |  |
| 3 | No |  |
| 4 | No family or friends were involved |  |
| 5 | My family or friends didn't want or need information |  |

For the following questions that ask about medicines/medications, please take this to mean any treatments (including but not limited to radiotherapy and surgery) that you may have received for your skin cancer:

14. Did a member of staff explain the purpose of the medicines you were to take at home in a way you could understand?

- 1 Yes, completely
- 2 Yes, to some extent
- 3 No
- 4 I didn't need an explanation
- 5 I had no medicines - go to question 15

15. Did a member of staff tell you about medication side effects to watch for when you went home?

- 1 Yes, completely
- 2 Yes, to some extent
- 3 No
- 4 I didn't need an explanation

16. Did someone tell you about danger signals regarding your illness or treatment to watch for after you went home?

- 1 Yes, completely
- 2 Yes, to some extent
- 3 No

Patient Reported Toxicities

Date Completed:

D	D	M	M	Y	Y	Y	Y
---	---	---	---	---	---	---	---

1. Did your squamous cell skin cancer affect your head or neck region (this includes your scalp, face, ears or neck)?

a. Yes – please complete **both sections** of this questionnaire (all 20 questions)

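### The PPE-15 form in Appendix 1 prints the doctor question twice, so it runs to 16 items and the skip at item 14 skips nothing

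*Protocol*

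**What the plan says.** Protocol Section 5.4 lists the PPE-15 among the quality-of-life secondary outcomes. Section 14.3 and Table 2 schedule it once, at 12 months. Section 18.2 has patients complete it on paper, with site staff then entering it in REDCap.

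Appendix 1 prints the form. The points that matter are:

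- Item 1: "1. When you had important questions to ask a doctor, did you get answers that you could understand". It offers three answers: always, sometimes, and no.
- Item 2: "2. When you had important questions to ask a doctor, did you get answers that you could understand". It offers the same three answers and a fourth, "4. I had no need to ask".
- A note before item 14 says how to understand medicines: "please take this to mean any treatments (including but not limited to radiotherapy and surgery) that you may have received for your skin cancer".
- Item 14, fifth option: "I had no medicines - go to question 15".
- The next item: "15. Did a member of staff tell you about medication side effects to watch for when you went home".
- The last item: "16. Did someone tell you about danger signals regarding your illness or treatment to watch for after you went home".

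**The concern.** Two things on the form do not fit together. The same doctor question appears under two numbers with two sets of answers, and a routing instruction points to the item the patient would reach anyway.

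The first means that one patient can give two different answers to one question. A patient who had nothing to ask a doctor has no fitting answer on item 1 and has to leave it blank or choose one that does not apply. The Protocol does not say which of the two items counts.

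The second means that a patient who reports having had no medicines is led to a question about the side effects of medicines. That item offers two grades of yes, a no, and an option for not needing an explanation. It has no option for having had no medicines, so an answer given there could be read as a report about care that was never relevant.

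The form is used once, so a later administration cannot supply a clean answer. It is completed on paper, and Section 14.3 allows it to be posted back after a remote visit, so neither electronic branching nor a member of staff can be relied on to correct the route while the patient fills it in.

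**Working it through.** There is no power or error-rate calculation here. The check is a count of items and a trace of the skip, using only Appendix 1 and the name of the instrument.

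**1. Count.** The name implies 15 items. The printed numbers run from 1 to 16 without a gap. 16 − 15 = 1 surplus item.

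**2. Which item is surplus.** Items 1 and 2 have identical stems. No other pair does.

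**3. Is it an artefact of reading the PDF?** No. The two copies have separate numbers and different answer sets, and the later numbering runs on consistently to 16. A repeated text block would not do that.

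**4. Trace of the skip as printed.** A patient ticks the fifth option of item 14 and goes to 15. Items strictly between 14 and 15: 15 − 14 − 1 = 0. Nothing is skipped.

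**5. Trace after removing one doctor item.** Every later number falls by one:

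| Content | Printed number | Number with one doctor item removed |
|---|---|---|
| Purpose of medicines (contains the skip) | 14 | 13 |
| Medication side effects | 15 | 14 |
| Danger signals | 16 | 15 |

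The unchanged instruction to go to question 15 now starts from 13. Items strictly between: 15 − 13 − 1 = 1, the side-effects item. The patient lands on danger signals, a question that applies whether or not medicines were given. One cause, the extra doctor item, explains both the count of 16 and the dead skip.

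**6. Which copy to keep.** The parallel question about nurses, printed item 3, has four answers including the no-need-to-ask option. Printed item 2 has the same four and item 1 does not. Within the document, item 2 is the consistent version. The source instrument is not reproduced, so this should be confirmed against it.

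**7. Who is affected by the failed skip.** Inclusion criterion 1 in Section 8.1 requires an excised tumour, so every participant in both arms has had surgery. The note before item 14 counts surgery and radiotherapy as medicines. A patient who follows it should not tick the no-medicines option. Some still may, because the stem of item 14 speaks of medicines to be taken at home, which describes neither treatment well. The documents give no figure for how many.

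**The case against.** The strongest reply is that this is a proofreading slip that costs almost nothing. The failed skip loses no data: it collects one unneeded answer, and the tick at item 14 identifies exactly whose answer is unneeded. The duplicate adds one redundant response. Scoring of the PPE-15 may be set out in the statistical analysis plan, which is not shown. Most of this stands, and it limits the consequence. It does not make the printed form right: patients still see the same question twice, and a patient with no questions for a doctor still has no fitting answer on the first copy.

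Three stronger readings are tempting, and the documents support none of them.

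- *That the side-effects item is inflated by a material amount.* A figure would need the share ticking no medicines and the share of those then answering no. The Protocol gives neither. The form's definition of medicines points to a small first share, and the option for not needing an explanation gives those patients another answer to choose.
- *That the arms are biased against each other because only one receives radiotherapy.* The definition names surgery as well as radiotherapy, and both arms have had surgery. Under the printed wording the option should be rare in both.
- *That answers already collected cannot be repaired.* They can, from item 14.

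**Conclusion.** The point holds as a defect in a patient-facing form. The duplicate question, the 16 numbered items and the skip that bypasses nothing can all be read directly from Appendix 1.

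Its weight is minor. It touches one secondary questionnaire at one visit. The primary endpoint, the interim analyses, the main quality-of-life comparison (Section 17.3, global health status at 4 months) and the economic evaluation do not depend on it. The definite effects are two possibly conflicting answers to the doctor question and no fitting answer on item 1 for some patients. The possible effect is a probably small number of inapplicable answers on the side-effects item, all identifiable.

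Two assumptions remain. One is that the 15 in the instrument's name is its item count, which the skip target supports. The other is that the form in use matches the one printed. The REDCap entry form is not shown, so nothing can be said about whether it repeats the error.

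**What to change.** 1. Check the printed form against the source instrument.
2. Remove the duplicate doctor item. The copy with the no-need-to-ask option is the one to keep, subject to step 1, because it matches the nurse item.
3. Renumber the remaining items 1 to 15. The skip wording can then stay as it is, because question 15 becomes the danger-signals item.
4. Check that the REDCap entry form has the same items, numbers and answers.
5. For any forms already completed on the 16-item version, state in the analysis plan that only the retained doctor item is used, and that the side-effects item is set to not applicable where the patient reported no medicines at item 14.

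The cost is a corrected questionnaire version, a check and possible update of the entry form, and one sentence on handling earlier forms. No extra data, visits or participants are needed. The correction is best made before the first 12-month visits. The amendment table in Section 1 of this version is empty, so that may still be possible, though the Protocol does not state how far recruitment has gone.

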17.3 Quality of Life (QoL)

QoL improvement will be assessed primarily using the global health status derived from the EORTC QLQ-C30 questionnaire at 4 months from baseline (change from baseline in global health status score) between the two arms. This will be calculated as per scoring instructions in the EORTC QLQ-C30 manual. For analyses, descriptive statistics will be produced, using medians and interquartile ranges (IQRs) instead of means and standard deviations in cases of heavily skewed data. The standardized Skin Cancer Index questionnaire will be analysed, and missing data handled in accordance with their respective guidelines. Proportion of patients experiencing a change from baseline for each measure as well as mean group changes will be calculated. Associations between the reporting of skin toxicity due to radiotherapy between clinicians and patients (using CTCAE, v5.0) at the same timepoints will be explored. In addition, sub-group analyses based on age, gender, treatment arm, will be undertaken. Statistical significance tests will be carried out if clinically significant differences are observed. Independent samples t-tests will be used to compare means, and the nonparametric equivalent will be used to compare medians in the case of skewed data. Proportions will be compared using the chi-square test. Associations will be explored using multivariate regression analyses if sample size allows.

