b. No – please skip to **section 2** of this questionnaire and only answer questions 14-20

Section 1 – Please only complete this section if your squamous cell skin cancer affected your head or neck region. For each question, please tick the option you feel best describes the degree to which you experienced the symptom described. If you did not experience the symptom, please tick the None/Never option.

1. PRO-CTCAE® Symptom Term: Dry mouth

In the last 7 days, what was the SEVERITY of your DRY MOUTH at its WORST?

1. None

2. Mild

3. Moderate

4. Severe

5. Very Severe

2. PRO-CTCAE® Symptom Term: Difficulty swallowing

In the last 7 days, what was the SEVERITY of your DIFFICULTY SWALLOWING at its WORST?

1. None

2. Mild

3. Moderate

4. Severe

5. Very Severe

3. PRO-CTCAE® Symptom Term: Taste changes

In the last 7 days, what was the SEVERITY of your PROBLEMS WITH TASTING FOOD OR DRINK at their WORST?

1. None

2. Mild

3. Moderate

4. Severe

5. Very Severe

4. PRO-CTCAE® Symptom Term: Rash

In the last 7 days, did you have any RASH?

1. Yes

2. No

5. PRO-CTCAE® Symptom Term: Skin dryness

In the last 7 days, what was the SEVERITY of your DRY SKIN at its WORST?

1. None

2. Mild

3. Moderate

4. Severe

5. Very Severe

6. PRO-CTCAE® Symptom Term: Hair loss

In the last 7 days, did you have any HAIR LOSS?

1. Not at all

2. A little bit

3. Somewhat

4. Quite a bit

5. Very much

7. PRO-CTCAE® Symptom Term: Itching

In the last 7 days, what was the SEVERITY of your ITCHY SKIN at its WORST?

1. None

2. Mild

3. Moderate

4. Severe

5. Very Severe

8. PRO-CTCAE® Symptom Term: Hives

In the last 7 days, did you have any HIVES (ITCHY RED BUMPS ON THE SKIN)?

1. Yes

2. No

9. PRO-CTCAE® Symptom Term: Sensitivity to sunlight

In the last 7 days, did you have any INCREASED SKIN SENSITIVITY TO SUNLIGHT?

1. Yes
2. No

10. PRO-CTCAE® Symptom Term: Radiation skin reaction

In the last 7 days, what was the SEVERITY of your SKIN BURNS FROM RADIATION at their WORST?

1. None
2. Mild
3. Moderate
4. Severe
5. Very Severe

11. PRO-CTCAE® Symptom Term: Skin darkening

In the last 7 days, did you have any UNUSUAL DARKENING OF THE SKIN?

1. Yes
2. No

12. PRO-CTCAE® Symptom Term: Watery eyes

a. In the last 7 days, what was the SEVERITY of your WATERY EYES (TEARING) at their WORST?

1. None
2. Mild
-

3. Moderate

4. Severe

5. Very Severe

b. In the last 7 days, how much did WATERY EYES (TEARING) INTERFERE with your usual or daily activities?

1. Not at all

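### All prompted patient-reported skin items, including radiation skin reaction, are reserved for head-and-neck patients, so the structured patient-reported skin data cannot cover tumours elsewhere

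*Protocol*

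**What the plan says.** The Patient Reported Toxicities form in Protocol Appendix 1 begins by asking whether the cancer was on the head or neck, which it defines to include scalp, face, ears and neck. A patient who answers yes completes all 20 items. A patient who answers no is told to go to section 2 "of this questionnaire and only answer questions 14-20". The heading of the first section repeats the restriction: "Section 1 – Please only complete this section if your squamous cell skin cancer affected your head or neck region".

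The restricted section holds the skin items, from "4. PRO-CTCAE® Symptom Term: Rash" through "10. PRO-CTCAE® Symptom Term: Radiation skin reaction" to "11. PRO-CTCAE® Symptom Term: Skin darkening". The radiation item reads "In the last 7 days, what was the SEVERITY of your SKIN BURNS FROM RADIATION at their WORST".

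Elsewhere the protocol uses patient-reported toxicity without any limit by tumour site. Section 5.4 defines the safety outcome by CTCAE v5.0 and serious adverse events, "including patient-reported outcomes version of the CTCAE". Section 17.3 plans to explore "Associations between the reporting of skin toxicity due to radiotherapy between clinicians and patients" at matching timepoints.

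**The concern.** The routing treats skin symptoms as if they belonged to the head and neck. Dry mouth, swallowing, taste, watery eyes and nosebleed do depend on that site. Rash, dryness, itching, hives, sun sensitivity, radiation skin reaction and darkening can arise wherever skin is irradiated. The lay summary (section 3.3) names short-term skin inflammation and possible long-term discolouration in the treated area as the side effects of radiotherapy.

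The stake is coverage. A patient irradiated on the trunk or a limb who follows the form is never prompted about the reaction that the treatment is most expected to cause. This is a loss of data at collection, so an analysis plan cannot repair it later. The items ask about the last 7 days, and a missed answer cannot be recovered afterwards.

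**Working it through.** The protocol states no figure to reproduce here. The check compares the form, item by item, with eligibility, the other questionnaires and the planned analyses.

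**1. Item allocation (Appendix 1).**

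| Part of form | Who completes it | Items | Skin items |
|---|---|---|---|
| Section 1, items 1–13 | Head and neck only | Dry mouth, swallowing, taste, rash, dryness, hair loss, itching, hives, sun sensitivity, radiation skin reaction, darkening, watery eyes, nosebleed | 4, 5, 7, 8, 9, 10, 11 = 7; with hair loss (6) = 8 |
| Section 2, items 14–20 | Everyone | Pain, fatigue, anxiety, discouragement, sadness, libido, free-text other | 0 |

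13 + 7 = 20 items, which matches the form's own total. A patient with a tumour outside the head and neck is asked 0 of the 7 (or 8) structured skin items.

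**2. Are such patients eligible?** Yes. Section 8.1 sets no anatomical site. Exclusion 3 in section 8.2 removes only sites unsuitable for radiotherapy, with lip, eyelids, breast and anogenital area as examples. The form's own 'no' branch shows that other sites are expected.

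**3. Does another patient questionnaire fill the gap?** No. The EQ-5D and QLQ-C30 have no skin-symptom item. The Skin Cancer Index asks about worry, embarrassment, scarring and appearance, not skin reactions.

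**4. How often does the gap recur?** Table 2 schedules the form at baseline, at the end of weeks 2, 4 and 6 of radiotherapy (as the regimen requires), at 7 weeks in the comparator arm, and at 4, 8, 16, 24 and 36 months. Under full follow-up:

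- comparator arm: 1 + 1 + 5 = 7 forms
- radiotherapy arm: 1 + 1 + 5 = 7, 1 + 2 + 5 = 8 or 1 + 3 + 5 = 9 forms for the 2-, 4- and 6-week regimens.

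Both the acute and the late period are affected.

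**5. What depends on these items?**

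- The patient-reported part of the secondary safety outcome (section 5.4), as far as it concerns skin.
- The clinician-patient comparison in section 17.3. It needs a pair of reports at the same timepoint. Outside the head and neck the clinician half exists and the structured patient half does not.

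**6. How many patients?** The count would be 840 × (share with tumours outside the head and neck). The protocol does not give that share, so the count cannot be computed. For each such patient who follows the form, all of the structured skin items are missing.

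**The case against.** The strongest reply is that skin toxicity is still measured in these patients, and that reply stands. Table 2 schedules clinician-reported toxicity at the same visits as the patient form, and the section on assessments during radiotherapy requires both, with no limit by tumour site. The surgical site is examined throughout follow-up. Item 20 lets every patient list up to five other symptoms with a severity grade, and item 14 asks everyone about pain. A reader might infer from the routing that skin toxicity is never recorded for trunk or limb patients. The documents do not support that. What is missing is the prompted, graded patient report. Unprompted free text is not comparable with it, and clinician grades cannot supply the patient side of a clinician-patient comparison.

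A reader might also infer that the arms are compared unfairly. They are not: the skip depends on tumour site, which is fixed before randomisation, and it applies equally in both arms. The comparison within head-and-neck patients remains valid.

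It is also tempting to put a number on the harm. An assumed share of 20% to 40% outside the head and neck would give 840 × 0.20 = 168 to 840 × 0.40 = 336 patients, but nothing in the protocol supports that share. A claim that skin toxicity rates would be understated by the same percentage needs two further assumptions: that blanks are scored as no symptom, and that rates are equal across body sites. The protocol states neither, and it leaves missing-data handling to the SAP.

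Finally, section 17.3 describes the clinician-patient analysis as exploratory, and hair loss can reasonably be seen as a head-and-neck item because the form's definition includes the scalp. Both points are fair. They limit the weight of the finding and put the undisputed item count at 7.

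**Conclusion.** The routing error is plain on the face of the form and does not depend on any numerical assumption. Eligible patients with tumours outside the head and neck are asked none of the 7 structured skin items (8 with hair loss) at any scheduled visit. The structured patient-reported skin results and the section 17.3 comparison will therefore describe head-and-neck patients only, although the protocol sets no such limit on either.

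The consequence is loss of coverage in one component of a secondary outcome and in one exploratory analysis. The clinician-graded safety comparison, serious adverse event reporting, the primary endpoint and the sample size are untouched. This should be fixed, and promptly, because each completed visit loses answers for good. It does not threaten the trial's main conclusion. The only assumption is that patients and sites follow the form as printed.

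**What to change.** - Move the skin items that do not depend on body site (4, 5 and 7 to 11, and arguably 6) into the section that all patients complete.
- Keep dry mouth, swallowing, taste, watery eyes and nosebleed as head-and-neck items.
- Renumber the items, and correct the skip instruction and the matching REDCap form.
- On forms already completed, code the moved items as 'not asked' for patients with tumours elsewhere, so that a routed blank cannot be read as absence of the symptom.

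The cost is one reissued questionnaire with its REDCap form, and about 7 to 8 extra tick-box items per visit for patients outside the head and neck. Treatment, visit schedule, sample size and primary analysis do not change.
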